5.4.6.1 Hepatic Safety

For liver-associated enzymes and total bilirubin (TB), the number and percent of patients with abnormal values for ALT ($> 3 \times \text{ULN}$, $> 5 \times \text{ULN}$), AST ($> 3 \times \text{ULN}$, $> 5 \times \text{ULN}$), and TB ($> 2 \times \text{ULN}$) will be summarized by overall, normal baseline ALT/AST/TB and abnormal baseline ALT/AST/TB for overall safety population and patients who were on simvastatin 40mg or higher dose at any time during the study.

Hy's law criteria ($> 3 \times$ upper limit of normal [ULN] for either ALT or AST, with accompanying TB $> 2 \times \text{ULN}$) will also be applied to the data; any potential Hy's law cases will be listed.

A separate listing for direct TB will be provided for those who have Gilbert's syndrome.

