#### Hepatic Safety

Liver-associated enzymes and TB will be summarized by the value and change from baseline in the value, by treatment group and visit. In addition, the number and percent of patients with abnormal values for ALT, AST, and TB will be summarized. These summaries of patients with abnormal values will be performed overall; by normal baseline; and by abnormal baseline for each of ALT, AST, and TB. Hy's law criteria ( $\geq 3 \times \text{ULN}$  for either ALT or AST, with accompanying TB  $> 2 \times \text{ULN}$ ) will also be applied to the data; any potential Hy's law cases will be listed separately. *In the case of patients with Gilbert's disease, TB will be fractionated and the determination of  $2 \times \text{ULN}$  will be based upon direct (conjugated) bilirubin.*

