7. Uncontrolled hypertension, defined as sitting systolic blood pressure (SBP)  $\geq 160 \text{ mmHg}$  and diastolic blood pressure (DBP)  $\geq 100 \text{ mmHg}$  after sitting quietly for 5 minutes. Note: If the initial blood pressure (BP) values meet or exceed the specified level, an additional BP assessment may be completed. If the systolic or the diastolic values continue to meet or exceed the threshold, the patient may not continue screening. However, at the discretion of the Investigator, the screening period may be extended up to 2 weeks to allow for a repeat qualifying BP assessment following adjustment of BP medication(s), provided that the patient has been on a stable dose of the BP medication for a minimum of 2 weeks prior to randomization and the repeat BP measurements do not meet the exclusion criteria
8. Hemoglobin A1C (HbA1C)  $\geq 10\%$  at Week -2 (Visit S1)
9. Uncontrolled hypothyroidism, including thyroid-stimulating hormone (TSH)  $>1.5 \times$  the upper limit of normal (ULN) at Week -2 (Visit S1). Patients stabilized on thyroid replacement therapy for at least 6 weeks prior to randomization are allowed.

10. Liver disease or dysfunction, including:

- Positive serology for hepatitis B surface antigen (HBsAg) and/or hepatitis C antibodies (HCV-AB) at Week -2 (Visit S1); or
- Alanine aminotransferase (ALT), aspartate aminotransferase (AST)  $\geq 2 \times$  ULN, and/or total bilirubin (TB)  $\geq 1.2 \times$  ULN at Week -2 (Visit S1).

*Note: If HCV-AB is positive, a reflex HCV RNA will be performed to rule out active disease. Patients without active disease may be enrolled in the study.*

Note: At the discretion of the investigator, the screening period may be extended up to 2 weeks for a single repeat of ALT, AST, and/or TB. For those patients who have a repeat ALT, AST, and/or TB, the repeat value will be used to determine eligibility.

*If TB  $\geq 1.2 \times$  ULN, a reflex indirect (unconjugated) bilirubin will be obtained and if consistent with Gilbert's disease, the patient may be enrolled in the study.*

11. Gastrointestinal conditions or procedures (including weight loss surgery; eg, Lap-Band® or gastric bypass) that may affect drug absorption
12. Hematologic or coagulation disorders or a hemoglobin (Hgb) level  $< 10.0$  g/dL (100 g/L) at Week -2 (Visit S1)

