The SAP will supersede the protocol in the event of any differences between the two documents in the plans for data analysis, and the protocol will be amended if appropriate. The SAP will be included as an appendix in the clinical study report for this protocol.

3 Study Objectives and Endpoints

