5.4.6 Laboratory Evaluations

Continuous laboratory parameters (serum chemistry, hematology, coagulation (only at screening after amendment 3 and for those patients receiving anti-coagulation), urinalysis, urinalysis [microscopic]) listed in Table 4; fasting serum glucose, and HbA1c will be summarized using descriptive statistics for the observed value and the change from baseline by history of diabetics. Missing values for any of the laboratory evaluations will not be imputed; that is, only observed case data will be used. Baseline is defined as the last value prior to the first dose of study medication. Categorical urinalysis data will be listed, but will not be summarized.

As part of the AESI evaluation, below safety lab abnormality will be summarized by treatment group. All post-baseline lab values are being considered. Further details are provided in Section 5.4.6.1 through 5.4.6.4.

- ALT or AST (> 3x ULN and >5xULN)
- TB (> 2x ULN)
- Potential Hy's Law case: (ALT and/or AST > 3xULN with concurrent TB > 2xULN)
- CK (> 5x ULN) and (>10x ULN)
- Fasting Serum Glucose (mg/dL) (≤ 50 , and ≥ 126) by history of diabetics
- HbA1C ($\geq 6.5\%$) by history of diabetics
- Creatinine (change from baseline for >1 mg/dL)
- eGFR (< 15 mL/min/1.73m², 15 < 30 mL/min/1.73m²)
- Hgb (g/dL) (decrease from baseline for ≥ 2 g/dL)
- Hgb (<8 g/dL)

Table 4: Clinical Laboratory Parameters (Safety)

Hematology 
 • Hematocrit (Hct) • Hemoglobin (Hgb) • Mean corpuscular hemoglobin (MCH) • Mean corpuscular hemoglobin concentration (MCHC) • Mean corpuscular volume (MCV) • Platelet count • Red blood (RBC) cell count • White blood (WBC) cell count with differential (absolute and %) 	Blood Chemistry (serum, fasting) 
 • Albumin (Alb) • Alkaline phosphatase (Alk-P) • Alanine aminotransferase (ALT; SGPT) • Aspartate aminotransferase (AST; SGOT) • Blood urea nitrogen (BUN) • Calcium (Ca) • Carbon dioxide (CO₂) • Chloride (Cl) • Creatinine • Creatine kinase (CK) • Glucose • Lactate dehydrogenase (LDH) • Phosphorus • Potassium (K) • Sodium (Na) • Total and direct bilirubin (TB) • Total protein • Uric acid

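### The SAP's Hy's law criterion omits the protocol's direct-bilirubin rule for patients with Gilbert's disease, and the change is not declared

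*SAP*

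**What the plan says.** **Eligibility.** Under exclusion criterion 10 in Protocol 7.2, screening total bilirubin of 1.2 × ULN or more excludes a patient, with an exception: "a reflex indirect (unconjugated) bilirubin will be obtained and if consistent with Gilbert's disease, the patient may be enrolled in the study". The synopsis has the same provision.

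**Protocol analysis text.** The Hepatic Safety paragraph in the synopsis statistical methods defines Hy's law by an aminotransferase limit together with total bilirubin above 2 × ULN. It goes on to say that in patients with Gilbert's disease "TB will be fractionated and the determination of" 2 × ULN "will be based upon direct (conjugated) bilirubin". Protocol 11.1.6.3.1 has the same note for monitoring individual patients.

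**SAP.** Section 5.4.6.1 fixes the meaning of TB as total bilirubin: "For liver-associated enzymes and total bilirubin (TB), the number and percent of patients with abnormal values for ALT", and likewise for AST and TB. Section 5.4.6 defines a potential Hy's law case as "ALT and/or AST > 3xULN with concurrent TB > 2xULN", to be summarised by treatment group. Section 5.4.6.1 repeats the criterion and lists the cases. Neither place has an exception for Gilbert's disease. Section 5.4.6.1 ends with the one provision for these patients: "A separate listing for direct TB will be provided for those who have" Gilbert's syndrome.

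**Precedence.** SAP section 2 states: "The SAP will supersede the protocol in the event of any differences between the two documents in the plans for data analysis". Protocol 12.1 agrees. SAP 4.6 names three changes from the protocol (added subgroup and sensitivity analyses, the clarification of objectives, and the multiplicity adjustment). None concerns bilirubin.

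**The concern.** The protocol admits patients whose total bilirubin may be raised for a reason unrelated to drug injury, and it adjusts its Hy's law criterion for them. The SAP keeps the criterion, leaves out the adjustment and takes precedence. An analyst who follows the SAP would tabulate and list a case that the protocol's own definition does not recognise.

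This matters because safety is the primary endpoint and SAP 5.4.6 places the Hy's law count within the evaluation of adverse events of special interest. Such cases are usually few and are read one at a time, so the criterion should be settled before the data are seen. The omission looks unintended. Item 3 of the SAP summary of changes says the laboratory section was updated for the hepatic language of Amendment 3, which is the amendment that added the Gilbert's sentence to the protocol's statistical text.

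**Working it through.** The plan states no figure on this point, so the check compares the two definitions.

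**Step 1: does the protocol rule belong to the analysis?** Yes. It stands in the statistical methods, directly after the Hy's law criterion. It is not only a monitoring instruction.

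**Step 2: are these patients in the trial?** Yes, by design. Someone admitted through the Gilbert's exception had screening total bilirubin of at least 1.2 × ULN. That is 1.2 / 2 = 0.60, or at least 60% of the way to the 2 × ULN line on total bilirubin.

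**Step 3: apply both definitions.** Take patients with ALT or AST above 3 × ULN. (The protocol writes this limit as at least 3 × ULN and the SAP as above 3 × ULN. That is a separate discrepancy, and values above 3 satisfy both.)

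| Patient | Total bilirubin | Direct bilirubin | Protocol | SAP |
|---|---|---|---|---|
| No Gilbert's disease | > 2 × ULN | any | case | case |
| Gilbert's disease | > 2 × ULN | > 2 × ULN | case | case |
| Gilbert's disease | > 2 × ULN | ≤ 2 × ULN | not a case | case |
| Gilbert's disease | ≤ 2 × ULN | ≤ 2 × ULN | not a case | not a case |

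The definitions part in the third row. The direct-bilirubin listing does not change the SAP entry in that row, because it feeds neither the count nor the flag.

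**Step 4: which document governs?** The SAP, under its section 2 and Protocol 12.1. The third-row patient is therefore reported as a potential Hy's law case.

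**Step 5: does the conflict extend to the stand-alone bilirubin table?** No. For that table the protocol speaks only of abnormal values and sets no 2 × ULN cut-off. In the protocol paragraph, 2 × ULN appears only in the Hy's law criterion and in the Gilbert's sentence that follows it. The table's 2 × ULN threshold comes from the SAP, so no protocol rule was removed from it.

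**Step 6: how many patients?** This cannot be computed. It would need the frequency of Gilbert's disease among those randomised, their bilirubin distribution, and how often an aminotransferase rise coincides. The documents give none of these.

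**The case against.** The strongest reply is that the SAP uses a sensitive screen and supplies what is needed to resolve it. Cases are labelled potential and are listed individually, and direct bilirubin is listed for the patients in question, so a reviewer can set a third-row case aside from planned output. Gilbert's disease precedes randomisation, so apart from chance it does not favour either arm. The SAP's change summary (item 15) says abnormal laboratory cut-offs were revised in the light of recent data and DMC advice, so the choice may have been deliberate. The direct-bilirubin note in Protocol 11.1.6.3.1 is untouched, because the SAP overrides only analysis plans.

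Much of this stands, and it limits the consequence. No data are lost and patient protection is unaffected. It does not remove the conflict. A listing from which the reader must correct the count is weaker than a prespecified criterion. Balance on average says little about a count of a few cases. If the departure was deliberate, SAP 4.6 is where it should have been declared. SAP 5.4.6.1 also splits the abnormal-value counts by normal or abnormal baseline, but that split is not described for the Hy's law cases and does not isolate patients with Gilbert's disease.

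A reader might infer three stronger things. One is that the stand-alone count of total bilirubin above 2 × ULN also breaks a protocol rule. It does not, because the protocol gives that table no such cut-off. Another is that the number of misclassified patients can be estimated from a population prevalence. That figure is not in the documents, and a general prevalence would ignore that, before Amendment 3, screening total bilirubin of 1.2 × ULN or more was exclusionary with no Gilbert's exception. The third is that a single false case would overturn the hepatic conclusion. With individual listings and direct bilirubin beside them, that is not shown.

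**Conclusion.** The point holds for the Hy's law criterion. The two documents classify one defined type of patient differently, the SAP version governs, and the change is not declared. The conclusion follows from the wording and needs no numerical assumption. Its size in patients is unknown and may be zero, because a discordant case needs Gilbert's disease, an aminotransferase above 3 × ULN with concurrent total bilirubin above 2 × ULN, and direct bilirubin that does not exceed 2 × ULN. The planned listing softens the effect. It is worth correcting because the output is a small count read case by case in a study whose primary endpoint is safety, and because the correction is cheap.

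**What to change.** In SAP 5.4.6 and 5.4.6.1:

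- Apply the protocol's direct-bilirubin determination to patients with Gilbert's disease in the potential Hy's law criterion, and say which upper limit of normal it uses.
- State how these patients are identified, for example from medical history or the screening reflex bilirubin result. The SAP does not say at present.
- Keep cases that meet the criterion on total bilirubin only as a footnoted listing with their direct values. Reword the phrase that pairs direct with TB, since TB means total bilirubin in that section.
- In the stand-alone table of total bilirubin above 2 × ULN, leave the threshold as it is and footnote how many of the counted patients have Gilbert's disease.

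If the sponsor prefers total bilirubin for everyone, SAP 4.6 should list this as a departure from the protocol and give the reason.

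The cost is SAP wording, one rule for identifying patients and a small programming change. No new samples are needed, because direct bilirubin is in the chemistry panel (Protocol Table 5, SAP Table 4) drawn with the safety laboratories. The downside is a slightly less sensitive Hy's law flag in patients with Gilbert's disease, which the footnoted listing covers.

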5.4.6.2 Musculoskeletal Safety

CK levels will be summarized by the value and change from baseline in the value, by treatment group and visit as well as baseline eGFR category. In addition, the number and percent of patients with abnormal CK values ($> 5 \times \text{ULN}$, $> 10 \times \text{ULN}$) will be summarized for overall safety population and patients who were on simvastatin 40mg or higher dose at any time during the study. These summaries of patients with abnormal CK will be performed overall, normal baseline CK, and abnormal baseline CK.

5.4.6.3 Diabetes and Glycemia

For fasting serum glucose and HbA1C (%), a shift table from baseline with the number and percent of patients will be categorized as below:

Fasting glucose: $\geq 126 \text{ mg/dL}$; $100\text{-}125 \text{ mg/dL}$, and $< 100 \text{ mg/dL}$; HbA1C (%): $\geq 6.5\%$; > 5.5 to $\leq 6.4\%$ and $\leq 5.5\%$. These tables will be summarized by history of Diabetes.

Descriptive summary for fasting serum glucose and HbA1C will be provided by history of diabetics and treatment group at each scheduled visit.

5.4.6.4 Renal Safety

By-visit summary and shift tables of eGFR by baseline category will be provided by treatment group.

In addition, renal function abnormality will be identified as: (1) A creatinine change from baseline of $> 1 \text{ mg/dL}$ (2) eGFR value $< 30 \text{ mL/min/1.73m}^2$. A shift table from baseline with the number and percent of patients using the two categories will be presented.

5.4.7 Physical Examinations (PEs)

Listings of PE data will include only those records where the body system at the baseline PE was normal, but the body system at a post-baseline PE was marked as 'Change from previous exam, clinically significant.' Only changes from baseline physical examination

findings that meet the definition of an AE will be recorded on the AE page of the eCRF and will be summarized with other AE outcomes.

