#### Primary Safety Endpoint

The primary endpoint for this study is general safety, which includes AEs, clinical safety laboratories, PEs, vital signs, and ECGs.

The summarization of AEs will include only treatment-emergent AEs (TEAEs), defined as AEs that begin or worsen after randomization and ingestion of the first dose of study drug. TEAEs and SAEs will be summarized by system organ class (SOC), severity, and relationship to study drug for each treatment group. Deaths, withdrawal from study treatment due to AEs, and withdrawal from the study due to AEs will each be summarized by treatment group.

Clinical safety laboratories, including hematology, blood chemistry, coagulation, HbA1C, glucose, and urinalysis; PE findings; vital signs; ECG readings; and weight will be summarized by the value and by change from baseline in the value (where appropriate) at each post-baseline time point.

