### **11.2.3. Reporting**

All AEs occurring during the course of the study (starting from signing informed consent to study completion) will be collected on the AE eCRF. Patients should be instructed to report any AE that they experience to the Investigator. Beginning with Visit S1 (Week -2), Investigators should make an assessment for AEs at each visit and record the event on the appropriate AE eCRF.

Wherever possible, a specific disease or syndrome rather than individual associated signs and symptoms should be identified by the Investigator and recorded on the eCRF. However, if an observed or reported sign or symptom is not considered a component of a specific disease or syndrome by the Investigator, it should be recorded as a separate AE on the eCRF. Additionally, the condition that led to a medical or surgical procedure (eg, surgery, endoscopy, tooth extraction, transfusion) should be recorded as an AE, not the procedure.

Any medical condition already present at screening or baseline should not be reported as an AE unless the medical condition or signs or symptoms present at baseline changes in severity or seriousness at any time during the study. In this case, it should be reported as an AE.

Clinically significant abnormal laboratory or other examination (eg, ECG) findings that are detected during the study or are present at baseline and significantly worsen during the study should be reported as AEs. The Investigator will exercise his or her medical and scientific judgment in deciding whether an abnormal laboratory finding or other abnormal assessment is clinically significant. Significant abnormal laboratory values occurring during the clinical study will be followed until repeat tests return to normal, stabilize, or are no longer clinically significant. Any abnormal test that is determined to be an error does not require reporting as an AE.

Each AE is to be evaluated for duration, severity, seriousness, and causal relationship to the investigational drug. For each AE, the following information will be recorded:

- Description of the event (eg, headache)
- Date of onset
- Date of resolution (or that the event is continuing)
- Action taken as a result of the event
- Seriousness of the event
- Severity of the event
- Outcome of the event
- Investigator's assessment of relationship to study drug.

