3.2 Primary Safety Endpoints

The primary safety endpoint for this study is general safety, which includes adverse events (AEs), clinical safety laboratories, physical examinations (PEs), vital signs, and electrocardiogram (ECGs).

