3.2.1 Adverse Events

The evaluation of AEs will include only incidence of treatment-emergent AEs (TEAEs), defined as AEs that begin or worsen after the first dose of IMP until 30 days after last dose of IMP. Clinical endpoints will be collected and adjudicated by an independent

Confidential

Page 7 of 33

Clinical Events Committee (CEC). Clinical endpoints will also be reported as SAEs. Adverse events of special interest (AESI) will further be examined (See Section 5.4.2 for more information).

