3.2.3 ECG, Vital Signs and PE

The evaluation of ECG and vital signs (including heart rate, systolic blood pressure, diastolic blood pressure, weight, height [baseline only], and body mass index [BMI]), will be based on the observed values. For ECGs, shifts from baseline to end-of-study will be summarized. For vital signs, observed values and changes from baseline will be summarized for all post-baseline study visits. Listings of PE data will include only those records where the body system at the baseline PE was normal, but the body system at a post-baseline PE was marked as 'Change from previous exam, clinically significant.'

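### The only output from the physical-examination form is a listing limited to body systems normal at baseline, with no count by arm, so a flagged worsening in an already abnormal system that is not also entered as an AE appears nowhere

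*SAP*

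**What the plan says.** SAP 3.2 defines the primary safety endpoint as general safety, "which includes adverse events (AEs), clinical safety laboratories, physical examinations (PEs), vital signs, and electrocardiogram (ECGs").

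For PE, SAP 3.2.3 and 5.4.7 set the same two-part rule for the listing. The first part is a baseline condition: "Listings of PE data will include only those records where the body system at the baseline PE was normal". The second is a post-baseline condition: "but the body system at a post-baseline PE was marked as 'Change from previous exam, clinically significant". Both must be met. The SAP describes no table, shift table or count of PE-form data.

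SAP 5.4.7 then gives a second route. PE changes that "meet the definition of an AE will be recorded on the AE page of the eCRF and will be summarized with other AE outcomes". This route carries no condition on baseline status.

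The synopsis of the protocol, under Primary Safety Endpoint, planned something different for the PE data: "PE findings; vital signs; ECG readings; and weight will be summarized by the value and by change from baseline in the value", with the qualifier that change from baseline applies where appropriate. It sets no baseline-normal restriction. SAP section 2 says that the SAP prevails where the two documents differ on analysis, so the filtered listing is the operative plan. SAP 4.6, which lists changes from the protocol's planned analyses, does not mention PE.

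**The concern.** The filter works on baseline status, not on the importance of the change. Two patients with the same investigator flag are treated differently: the one whose system was normal at baseline is listed, and the one whose system was already abnormal is not. In patients with established cardiovascular disease, some of whom enter with peripheral arterial disease or a past stroke with focal deficit, it is plausible that some systems are abnormal at baseline and that worsening there is of interest. The protocol synopsis also names PE findings, alongside AEs, as a means of identifying musculoskeletal and neurocognitive events.

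At stake is whether one named component of the primary safety endpoint has a complete output that can be compared between arms, and whether the PE form can serve as a cross-check on AE reporting.

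**Working it through.** No arithmetic in the plan is involved. The check is to trace where a change marked clinically significant on the PE form ends up, using four rules:

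1. The listing rule (SAP 3.2.3 and 5.4.7): baseline normal and post-baseline flag present.
2. The AE route (SAP 5.4.7): PE changes meeting the AE definition go to the AE page and the AE summaries.
3. The AE reporting rule (Protocol 11.2.3): clinically significant examination findings that "are present at baseline and significantly worsen during the study should be reported as AEs".
4. The treatment-emergent definition (SAP 3.2.1): "defined as AEs that begin or worsen after the first dose of IMP until 30 days after last dose of IMP". Worsening therefore counts. SAP 5.4.1 builds its tables on TEAEs and lists all AEs, with the others flagged.

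For a flagged PE change this gives four cases:

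| Baseline status of the system | Entered as an AE? | PE listing | AE outputs |
|---|---|---|---|
| Normal | Yes | Yes | Yes |
| Normal | No | Yes | No |
| Abnormal | Yes | No | Yes |
| Abnormal | No | No | No |

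Only the last row appears in no planned output. In the third row the event is reported, by arm if it is treatment-emergent and otherwise in the AE listing, but the PE flag behind it is not shown. Because rows three and four are both missing from the PE listing, a reader cannot tell them apart, and so cannot check whether flagged changes in baseline-abnormal systems were reported as AEs.

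Size, in symbols: let q be the share of flagged changes that arise in baseline-abnormal systems, and r the share of those not entered as AEs. The PE listing omits q of all flagged changes. The fraction missing from every output is q × r. With complete AE reporting r = 0 and the loss is 0; at the other extreme r = 1 and the loss is q. The documents give neither q nor r.

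Comparison with the rest of the SAP:

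- AEs (5.4.1), laboratory data (5.4.6), vital signs (5.4.8) and ECGs (5.4.9) all have by-arm output. PE data do not.
- ALT, AST and bilirubin abnormalities (5.4.6.1) and CK abnormalities (5.4.6.2) are summarized overall and separately for normal and abnormal baseline.
- The ECG listing (5.4.9) admits a baseline that is abnormal but not clinically significant, and a by-arm shift table stands beside it.

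PE is the only component for which every abnormal baseline is dropped with no table to compensate.

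**The case against.** A reader might infer that worsening of an already abnormal system is left out of the primary safety endpoint. The documents do not support that. The sentence after the filter in SAP 5.4.7 sends PE changes meeting the AE definition to the AE summaries, Protocol 11.2.3 tells sites to report significant worsening of a baseline finding as an AE, and the TEAE definition includes worsening. AEs are themselves a component of the endpoint and are tabulated by arm. For a flagged change to vanish, a site must mark it clinically significant and then not report it, contrary to 11.2.3. This part of the objection stands and sets the limit of the point.

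A reader might also infer that a fixed share of flagged changes is lost, equal to the share of patients with an abnormal baseline system. That confuses absence from one listing with absence from all output, and the documents give no baseline PE rates. Entry rests on history, testing or genotype, not on an abnormal examination.

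Two further arguments carry some weight. The protocol's PE summary was qualified by where appropriate, and categorical findings have no numerical change, so a listing is a defensible format. And the SAP is entitled to supersede the protocol. Neither explains why the listing excludes abnormal baselines, or why SAP 4.6 does not record the move from a summary to a filtered listing.

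**Conclusion.** The point holds in a limited form. The PE form feeds one output, a listing filtered to baseline-normal systems with no count by arm, although PE is a named part of the primary safety endpoint and the protocol synopsis planned a summary without that filter. Two consequences follow: a flagged change in a baseline-abnormal system that was not entered as an AE appears in no output, and flags in those systems cannot be reconciled with AE reporting. The undeclared departure from the protocol is a third, smaller matter.

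The size is q × r, cannot be estimated from the documents, and is small if sites follow Protocol 11.2.3. No hypothesis or decision rule depends on the PE data. The conclusion assumes that the PE form records both baseline status and the change flag by body system, as the SAP's own listing rule requires. This is an inexpensive improvement to the safety reporting, not a threat to the trial's conclusions.

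**What to change.** - In SAP 3.2.3 and 5.4.7, delete the baseline-normal condition. List every post-baseline PE record carrying the clinically significant change flag, and show for each the baseline status of that body system and whether a matching AE was recorded.
- Add one table of the number and percent of patients with such a change, by body system and arm, split by normal or abnormal baseline.
- In SAP 4.6, declare any remaining departure from the PE summary in the protocol synopsis.

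The cost is a few lines of SAP text, one filter removed, one link to the AE data and one small table. PE is already scheduled at T1 and at T7 or early withdrawal, and Protocol 10.2.8 adds withdrawal from study drug, so no new data collection is needed.
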